## **5.8. Analysis of Safety Data**

The analysis of safety and tolerance will be performed on the SAF, as defined in Section 3.4.

The safety analysis will be based on the reported AEs and other safety information (clinical laboratory evaluations, vital signs and 12-lead ECG).

Thresholds for Potential Clinically Significant Values (PCSV) in laboratory variables, vital signs and ECG are defined in Section 10.3.

The summary of safety results will be presented for each treatment group and by visit where applicable.

Day 1 is the first day of investigational product, Day –1 is the day before; there is no Day 0.

The time interval to detect any AEs, including AESIs (except JR identified at the 72-week telephone follow-up), or abnormalities is between the first dose of study drug dose up to the end of the Follow-Up Period (i.e., week 44/Early Termination). Any study drug-related SAEs occurring between the end of Follow-Up clinic visit and the End of Study will also be included. Data collected outside this interval will be excluded from the descriptive statistics and identification of abnormalities for laboratory evaluations, ECGs and vital signs. All post-baseline data during the interval will be used in the PCSV analysis including scheduled and unscheduled assessments.

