### **5.8.3. Clinical Laboratory Measurements**

Baseline clinical laboratory analytes and change from baseline in clinical laboratory analytes to each scheduled assessment time will be summarized with descriptive statistics for each treatment group.

Listings will be provided with flags indicating the out of laboratory range values.

A treatment-emergent Potential Clinically Significant abnormal value (PCSV) is a laboratory value that was normal or abnormal but not meeting PCSV criteria at Screening and Baseline but became abnormal and met PCSV criteria after treatment with study drug. Definitions of PCSV is listed in Section 10.3. Treatment-Emergent Potentially clinically significant values (PCSVs) will be summarized by treatment group.

For hs-CRP and alkaline phosphatase, plots of means and medians of the observed values and change from baseline over time will be presented by treatment group. Subgroup analysis will be performed for the following:

- Adjudicated Arthropathy category 1 (patients without / with AA)
- Adjudicated Arthropathy category 2 (patients without AA, patients with RPOA-1, and patients with other AA subtype except RPOA-1)
- Destructive Arthropathy category (patients without AA, patients with non-DA AA, patients with DA)

The above laboratory summaries will be constructed for the On-Treatment Period. Lab data collected during the Pre-Treatment and Post-Treatment Periods will be displayed in listings.

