#### **5.8.4. Analysis of Vital Signs**

Vital signs (blood pressure, temperature and respiration rate) will be summarized by baseline and change from baseline to each scheduled assessment time with descriptive statistics.

A treatment-emergent Potential Clinically Significant abnormal value (PCSV) is a vital sign value that was normal or abnormal but not meeting PCSV criteria at Screening and Baseline but became abnormal and met PCSV criteria after treatment with study drug. Definitions of PCSV is listed in Section 10.3. Treatment-Emergent Potentially clinically significant values (PCSVs) will be summarized by treatment group.

The incidence of confirmed measurements suggesting orthostatic hypotension will also be summarized by treatment group.

The above vital sign summaries will be constructed for the On-Treatment Period. Vital sign data collected during the Pre-Treatment and Post-Treatment Periods will be displayed in listings.

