#### **5.8.6. Physical and Neurological Examinations**

The percentage of patients with new-onset clinically significant abnormal physical examinations will be summarized by treatment group showing frequency and percentage by body system for each period as well as at the end of the period. Similarly summaries will be presented for neurological exam findings. These summaries will be constructed for the on-treatment period, post-treatment period and overall during the study.

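### SAP 5.8 runs the PCSV analysis to Week 44, but SAP 5.8.3 and 5.8.4 confine the laboratory and vital-sign PCSV tables to the On-Treatment Period, a narrowing of the protocol that SAP 1.2.4 does not declare

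*SAP*

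**What the plan says.** SAP 5.8 gives one interval for detecting adverse events and abnormalities: first dose to the end of follow-up, at Week 44 or early termination. It excludes data outside that interval and then states: "All post-baseline data during the interval will be used in the PCSV analysis including scheduled and unscheduled assessments".

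SAP 5.8.3 defines a treatment-emergent laboratory PCSV and says "Treatment-Emergent Potentially clinically significant values (PCSVs) will be summarized by treatment group". Further down it adds "The above laboratory summaries will be constructed for the On-Treatment Period", followed by "Lab data collected during the Pre-Treatment and Post-Treatment Periods will be displayed in listings".

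SAP 5.8.4 repeats the PCSV definition and summary for vital signs and adds a second output: "The incidence of confirmed measurements suggesting orthostatic hypotension will also be summarized by treatment group". It then limits the vital-sign summaries above it to the On-Treatment Period and says "Vital sign data collected during the Pre-Treatment and Post-Treatment Periods will be displayed in listings".

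SAP 5 ends the On-Treatment Period 28 days after the last dose of study drug. Protocol 10.4.4.2 asks for PCSVs at any post-randomization time point, for laboratory tests and for vital signs and ECG. SAP 1.2.4, which lists modifications from the protocol's statistical section, mentions no change to this window.

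**The concern.** The two instructions cannot both be programmed. A PCSV that first appears after the On-Treatment Period and before Week 44 counts in the treatment-group table under SAP 5.8, and is only listed under SAP 5.8.3 or 5.8.4. The reported between-group rates therefore depend on which sentence the programmer follows.

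The affected data will exist. Protocol 7.3.2 asks patients who stop study drug but stay in the study to attend all remaining visits. Protocol 7.3.2.1 moves certain patients enrolled under earlier versions straight into safety follow-up. The schedule of events places laboratory tests at Week 44 and orthostatic assessments at Weeks 28 and 44 for everyone. Protocol 9.6.1.2 uses the orthostatic assessment to monitor sympathetic nervous system dysfunction, an adverse event of special interest.

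**Working it through.** The plan states no figure to reproduce, so the check is a comparison of texts followed by date arithmetic.

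**Texts side by side**

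| Source | Output | Period |
|---|---|---|
| Protocol 10.4.4.2 | Laboratory, vital-sign and ECG PCSVs | Any time after randomization |
| SAP 5.8 | PCSV analysis | First dose to Week 44 or early termination |
| SAP 5.8.3 | Laboratory PCSVs | On-Treatment only; later data listed |
| SAP 5.8.4 | Vital-sign PCSVs and confirmed orthostatic hypotension | On-Treatment only; later data listed |
| SAP 5.8.5 | ECG PCSVs | No On-Treatment restriction stated |

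The general rule in SAP 5 applies unless otherwise stated. It does not settle the matter, because SAP 5.8 and SAP 5.8.3/5.8.4 each state a period of their own. The conflict is limited to laboratory tests and vital signs.

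Confirmed orthostatic hypotension needs separate treatment. SAP 4.6.5 defines it with a heart-rate rise and inability to stand as well as blood-pressure falls, whereas the PCSV row in SAP 10.3 has blood-pressure criteria only. The 5.8.4 incidence therefore conflicts with the general interval for abnormalities in SAP 5.8, not with the PCSV sentence itself.

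**Visits affected**

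Inputs:
- Target days from the schedule of events: Weeks 4, 8, 12, 16, 20, 24, 28 and 44 are Days 29, 57, 85, 113, 141, 169, 197 and 309.
- Post-baseline chemistry and hematology: Weeks 4, 16, 24, 44 (4 visits).
- Post-baseline orthostatic assessments: Weeks 4, 8, 12, 16, 20, 24, 28, 44 (8 visits).
- On-Treatment end day = day of last dose + 28 (SAP 5). A visit on the end day counts as on-treatment.

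SAP 5 does not say whether the last dose is the injection or the oral drug. Protocol 7.1 defines study drug to include both. Protocol 10.4.4 puts the last dose at Week 20, which suggests the injection, but the SAP does not repeat this. Both readings are shown.

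| Patient | Reading | On-Treatment end | Laboratory visits only listed | Orthostatic visits only listed |
|---|---|---|---|---|
| Last injected Week 8 | Injection | 57 + 28 = Day 85 | Weeks 16, 24, 44: 3 of 4 | Weeks 16, 20, 24, 28, 44: 5 of 8 |
| Last injected Week 8 | Oral to Day 85 | 85 + 28 = Day 113 | Weeks 24, 44: 2 of 4 | Weeks 20, 24, 28, 44: 4 of 8 |
| Completer | Injection | 141 + 28 = Day 169 | Week 44: 1 of 4 | Weeks 28, 44: 2 of 8 |
| Completer | Oral to Day 168 | 168 + 28 = Day 196 | Week 44: 1 of 4 | Weeks 28, 44: 2 of 8 |
| Completer | Oral to Day 169 | 169 + 28 = Day 197 | Week 44: 1 of 4 | Week 44: 1 of 8 |

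On the injection reading, a completer's Week 24 visit held after Day 169 but inside its 7-day window would also drop out.

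**The case against.** The best defence is that treatment-emergent already implies on-treatment: protocol 10.4.4.1 limits treatment-emergent adverse events that way, and SAP 5.8.3 and 5.8.4 are the more detailed sections. This does not hold. Those two sections give PCSVs their own definition, which requires onset after treatment with study drug and sets no end date. The sentence in SAP 5.8 is just as specific, since it concerns PCSVs by name. The protocol supports the wider window.

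Other objections limit how far the point goes, and they stand.

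- A reader might infer that orthostatic hypotension after treatment never reaches a between-group table. It can. Protocol 9.6.1.2 and SAP 6.3 have it recorded as an adverse event, and SAP 5.8.1 tabulates post-treatment adverse events by group. Sympathetic dysfunction events are summarized by group (SAP 5.8.2), and the Survey of Autonomic Symptoms at each scheduled visit (SAP 5.8.7). Laboratory PCSVs have no such automatic route; they become adverse events only under the criteria in protocol 9.4.5.
- A reader might infer that the losses fall mainly on patients who stopped because of an adverse event. The documents give no such share, and protocol section 1 reports a low rate of discontinuations due to adverse events.
- SAP 5.8.6 says of physical and neurological examinations: "These summaries will be constructed for the on-treatment period, post-treatment period and overall during the study". This shows that the three-period layout is in use. It does not show that orthostatic data must follow it: protocol 9.6.1.2 does not name the neurological examination among its monitoring tools for sympathetic dysfunction.
- The tables are descriptive, no hypothesis test depends on them, and the data are listed on either reading.

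**Conclusion.** The contradiction is real for laboratory and vital-sign PCSVs. If SAP 5.8.3 and 5.8.4 prevail, the SAP also departs from protocol 10.4.4.2 without saying so. Confirmed orthostatic hypotension is a separate output, confined in the same way and at odds with the interval for abnormalities in SAP 5.8. What drops out of the group comparison is the PCSV counts and the measurement-based orthostatic incidence after the On-Treatment Period, not all evidence of these events.

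The visit counts assume attendance on target days at all remaining visits and, on the oral reading, oral drug taken up to the next visit. They measure how much scheduled data moves to listings; the documents do not allow an estimate of how far the PCSV rates would change. Primary efficacy is unaffected. The period should be settled before unblinding, because it determines which between-group safety rates are reported.

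**What to change.** - In SAP 5.8.3 and 5.8.4, exempt treatment-emergent PCSVs and confirmed orthostatic hypotension from the On-Treatment restriction. Tabulate them by treatment group from first dose to Week 44 or early termination, with an on-treatment and post-treatment split like the one the adverse event tables in SAP 5.8.1 already have.
- In SAP 5, state whether the last dose that ends the On-Treatment Period is the SC injection or the oral drug.
- If a narrower window is preferred, amend SAP 5.8 to match and record the departure from protocol 10.4.4.2 in SAP 1.2.4.
- The by-visit mean-change summaries may stay On-Treatment.

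The cost is a few SAP sentences and extra columns in existing tables, which become slightly longer. No new data are needed.

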### **5.8.1. Adverse Events**

The verbatim text, the preferred term (PT), and the primary system organ class (SOC) will be displayed in subject listings. Summaries that include frequencies and proportions of patients reporting AEs will include the PTs and the SOCs.

For details on handling missing data and partial dates, see Section 6.3.

Summaries of AE incidence by treatment group will include:

- Overview of TEAEs, summarizing number of events, summarizing number and percentage of patients within the specified category
  - Total number of TEAEs
  - Total number of serious TEAEs
  - Total number of AESIs
  - Total number of serious AESIs
  - Patients with any TEAEs
  - Patients with any serious TEAEs

- Patients with any AESI's
- Patients with any serious AESIs
- Patients with any TEAEs leading to permanent study treatment discontinuation
- Patients with any TEAEs leading to withdrawal from study
- Patients with any TEAEs leading to death
- TEAEs by SOC and PT
  - All TEAEs
  - TEAEs by severity: mild, moderate or severe
  - TEAEs resulting in permanent study treatment discontinuation
- Study drug-related TEAEs by SOC and PT
  - All TEAEs
  - TEAEs by severity: mild, moderate or severe
  - TEAEs resulting in permanent study treatment discontinuation
- TEAEs by PT
  - All TEAEs
  - TEAEs resulting in permanent study treatment discontinuation
- Post-treatment AEs by SOC and PT
  - All post-treatment AEs
  - Post-treatment AEs by severity: mild, moderate or severe
- Serious TEAEs by SOC and PT
  - All serious TEAEs
- Post-treatment Serious AEs by SOC and PT
- All serious AEs on study by SOC and PT
- Non - Serious TEAEs by SOC and PT
  - All non-serious TEAEs
- Post-treatment Non-Serious AEs by SOC and PT
- All non-serious AEs on study by SOC and PT
- All AEs on study by SOC and PT
  - All AEs
  - All AEs by severity: mild, moderate or severe
- Deaths

Counts will be provided according to treatment group for each PT within each SOC. Percentages will be calculated using the number of patients in each treatment group using the respective SAF.

Primary SOCs will be sorted by descending frequency of the 'Fasimumab 1 mg SC Q4W' treatment group. Within each primary SOC, PTs will be sorted by decreasing frequency of investigational product.

A second type of table with counts of each primary SOC in decreasing order of frequency will be provided. A third type of table with counts of each PT in decreasing order of frequency will also be provided.

The following listings will be included:

- AEs leading to death
- TEAEs leading to permanent discontinuation from study treatment (not applicable to post-treatment AEs)
- TEAEs leading to withdrawal from study
- Patients with Serious TEAEs
- AESIs by AESI type
- Deaths
- All Joint Replacements
- Pre-treatment AEs
- Post-treatment AEs

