### 2.2. Sample Size and Power Considerations

Assuming a 2-sided alpha level of 0.05 and a 20% dropout rate up to week 24, an enrollment of 600 patients in the fasinumab 1 mg Q4W group and 300 patients in the placebo group will provide at least 99% power to detect an effect size of 0.46 in the WOMAC pain and physical function subscale scores (i.e., absolute treatment difference of 1.1 between fasinumab and placebo with a SD of 2.4). The assumed treatment difference and standard deviation (SD) are based on results from study R475-PN-1227. The sample size will provide 99% power to detect

an effect size of 0.36 in PGA (i.e., absolute treatment difference of 0.4 with a SD of 1.1, R475-PN-1227).

Assuming a 2-sided alpha level 0.05 and a 20% dropout rate up to week 24, an enrollment of 600 patients in the fasinumab 1 mg Q4W group and the pooled NSAIDs group will provide approximately 92% power to detect an effect size of 0.22 in the WOMAC pain subscale (i.e., absolute treatment difference of 0.51 with a SD of 2.3, [Schnitzer 2015]). The sample size will provide 95% power to detect an effect size of 0.24 in WOMAC physical function subscale (i.e., absolute treatment difference of 0.50 with a SD of 2.1, [Schnitzer 2015]), and 79% power to detect an effect size of 0.18 in PGA (i.e., absolute treatment difference of 0.18 with a SD of 1.0 [Ekman 2014]).

The sample size has been revised from 2700 patients in the previous amendments to approximately 1620 patients in amendment 4 due to the discontinuation of fasinumab 3 mg Q4W and 6 mg Q8W dose regimens. There will be approximately 600 patients randomized to the fasinumab 1 mg SC Q4W group, 300 patients randomized to the each of the NSAID groups, and 300 patients randomized to the placebo group (a total of 1500 patients). In addition, approximately 60 patients each were enrolled in the fasinumab 3 mg SC Q4W and 6 mg SC Q8W groups under earlier versions of the protocol before dosing was discontinued in these treatment groups.

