#### 3.4. The Safety Analysis Set (SAF)

The safety analysis set (SAF) includes all randomized patients from the FAS who received any study drug; it is based on the treatment received (as treated). Treatment compliance/administration and all clinical safety variables will be analyzed using the SAF including patients randomized to fasinumab 1 mg Q4W, NSAIDs, and placebo.

Determination of 'as-treated' will be performed in the following stepwise manner:

- If a patient receives at least one dose of fasinumab, 'as treated' implies the patients data will be analyzed under the fasinumab arm.
- If a patient receives no doses of fasinumab and was ever dispensed NSAIDs, 'as treated' implies the patients' data will be analyzed under the NSAID arm.
- If a patient receives no doses of either fasinumab or NSAID, the patients data will be analyzed under the placebo arm.

Safety data from patients randomized to fasinumab 3 mg Q4W or 6 mg Q8W will not be included in the main safety analysis summaries, but will be summarized in separate tables.

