## 5. STATISTICAL METHODS

For continuous variables, descriptive statistics will include the following: the number of patients reflected in the calculation (n), mean, median, standard deviation, minimum & maximum and 1st & 3rd quartiles (Q1 & Q3).

For categorical or ordinal data, frequencies and percentages will be displayed for each category.

**Period of Observation** - Unless otherwise stated, analysis of all safety and non-safety variables captured at multiple visits will be analyzed by the following observation periods:

- The Pre-Treatment Period is defined as the time from signing the ICF to before the first dose of study drug.
- The On-Treatment Period is defined as the time from the first dose of study drug up to 28 days after the last dose of study drug.
- The Follow-Up/Post-Treatment Period is defined from the end of the On-Treatment Period to the date of the follow-up clinic visit (Week 44 visit) or early termination date.

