### 5.3. Prior/Concomitant Medications

Summaries will present patient counts (and percentages) for all medications, dictionary coded by WHO, by decreasing frequency of the overall group incidence (or fasinumab 1mg Q4W group incidence in tables where the overall is not presented) of ATC followed by ATC level 2, ATC level 4 and preferred term. In case of equal frequency across anatomic or therapeutic categories, alphabetical order will be used. Patients will be counted once in each ATC category (anatomic or therapeutic) linked to the medication, but may be counted several times for the same medication.

The following will be summarized:

- All prior medications will be summarized by treatment group and overall, based on the SAF.
- All concomitant medications taken during the On-Treatment Period will be summarized by treatment group based on the SAF.

- All Post-treatment medications taken during the Post-Treatment period will be summarized by treatment group based on the subset of patients in the SAF.

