##### All-cause Joint Replacements

The number and percentage of patients with all-cause joint replacements will be presented by treatment group On-Treatment and Post-Treatment Periods based on the SAFs. The number of replacements in joints that were positively adjudicated will be summarized by treatment group. Joint replacements will also be summarized by KL score of the affected joint at screening.

Additionally, the number and percentage of patients who reported joint replacements at the End of Study Phone Call will be summarized.

The time to JR is calculated as:

$$= \text{Date of JR} - \text{Date of first dose of study drug} + 1$$

Plots of the Kaplan Meier curves by treatment group (as randomized) of time to JR will be presented based on the SAF, regardless of what period in the study the JR occurred. Patients without an event will be censored at the last contact.

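### Post-treatment AE and joint-replacement percentages are taken over everyone dosed, and no person-time rate shows the absent or unequal AE follow-up in that period

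*SAP*

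**What the plan says.** SAP 5.8.1 lists post-treatment AE tables (all, by severity, serious, non-serious) and gives one rule for AE percentages: "Percentages will be calculated using the number of patients in each treatment group using the respective SAF". SAP 3.4 defines a single SAF, "all randomized patients from the FAS who received any study drug". No period-specific version exists.

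SAP 5.8.7 treats joint replacement (JR) the same way: "The number and percentage of patients with all-cause joint replacements will be presented by treatment group On-Treatment and Post-Treatment Periods based on the SAFs". It adds that "the number and percentage of patients who reported joint replacements at the End of Study Phone Call will be summarized", without naming a denominator.

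The periods are set in SAP 5 (Period of Observation). On-treatment is "the time from the first dose of study drug up to 28 days after the last dose of study drug". Then: "The Follow-Up/Post-Treatment Period is defined from the end of the On-Treatment Period to the date of the follow-up clinic visit" at Week 44, or to the early termination date. Both limits are specific to the patient.

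For time to event, SAP 5.8.7 plans Kaplan-Meier curves for JR from first dose across all periods, censored at last contact, and Kaplan-Meier with Cox models for adjudicated arthropathy (AA) and destructive arthropathy (DA). SAP 5.8.2 gives the sympathetic and peripheral sensory AEs of special interest (AESIs) as incidence only. No exposure-adjusted AE rate is planned anywhere.

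**The concern.** A percentage for a period is easy to read as the risk in that period. Here the denominator includes patients who could not have had a recorded event in it, because they left the study within 28 days of the last dose. Among those who did enter, time at risk differs by a factor of two or more: Protocol 7.3.2 and 8.1.3 encourage patients who stop drug to stay, so an early stopper accumulates more post-treatment time than a completer.

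Events after stopping drug matter for this class of antibody. Equal stopping across arms should not be taken for granted either. Protocol 7.3.2.1 stops drug permanently for AA, JR, peripheral neurologic events and gastrointestinal bleeding, some of which the protocol links to anti-NGF antibodies and others to NSAIDs. If arms differ, the post-treatment AE tables can show a difference at equal risk, or hide a real one.

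**Working it through.** **Inputs.** Last SC dose at Week 20, day 141; Week 44 target day 309 (SAP Tables 1 and 2). On-treatment period ends at last dose + 28 days (SAP 5). Planning assumption: "a 20% dropout rate up to week 24" (SAP 2.2), not split by arm. Study drug includes the oral drug (Protocol 7.1).

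**Step 1: reproduce the plan's follow-up length.** 141 + 28 = 169; 309 − 169 = 140 days = 20.0 weeks, the stated follow-up period.

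**Step 2: post-treatment time by last SC dose, for a patient who stays to Week 44.** Days = 309 − (last dose day + 28).

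| Last SC dose (day) | 1 | 29 | 57 | 85 | 113 | 141 |
|---|---|---|---|---|---|---|
| Post-treatment days | 280 | 252 | 224 | 196 | 168 | 140 |

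A patient who leaves within 28 days of the last dose has 0. If the last oral dose counts (about day 168 or 169), a completer has 309 − 169 − 28 = 112 days, or 113. Protocol 10.4.4 places the last dose at Week 20, which points to the SC reading; the SAP definition does not say.

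**Step 3: understatement within an arm.** If a share q of the SAF never enters, percentage over SAF = (1 − q) × percentage among entrants. With q = 0.20 (every planned dropout leaves first) the factor is 0.80; with q = 0.10 it is 0.90.

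**Step 4: comparison between arms.** The arm-specific shares and the hazard are assumptions. The hazard is constant and equal in both arms, so the true ratio is 1: P(event in t days) = 1 − exp(−h·t/365.25). With h = 0.5 per year, P(140) = 17.44%, P(210) = 24.98% and P(280) = 31.84%.

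*Dropouts leave before the period:*
- 20% in both arms: 0.80 × 17.44 = 13.95% in each; ratio 1.00.
- 10% vs 30%: 15.70% vs 12.21%; ratio 0.90/0.70 = 1.29.
- 15% vs 25%: 14.82% vs 13.08%; ratio 0.85/0.75 = 1.13.

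*Stoppers stay, 10% vs 30%:*
- 210 days each: 0.90 × 17.44 + 0.10 × 24.98 = 18.19%, vs 0.70 × 17.44 + 0.30 × 24.98 = 19.70%; ratio 0.92.
- 280 days each: 18.88% vs 21.76%; ratio 0.87.

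At h = 0.03 per year the 10% vs 30% ratios are 1.29 (leave) and 0.91 to 0.85 (stay).

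**Step 5: what each remedy does.** Dividing by entrants only returns 1.00 when dropouts leave, but still gives 0.92 to 0.87 when stoppers stay. Patients with event per 100 patient-years gives 50 in both arms, ratio 1.00, in every scenario.

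**The case against.** The percentage of all treated patients with an observed event is a legitimate crude incidence and keeps the whole dosed population. The post-treatment AE tables are descriptive, no test rests on them, and Protocol 10.4.4.1 puts the focus on treatment-emergent events. SAP 5.8.1 also plans tables of all AEs on study, which remove the split by period. SAP 5.5.2 and 5.6.3 show discontinuation over time and length of observation by arm. JR, AA and DA have censored analyses. All of this stands, and it is why the SAF percentages should stay. But the whole-study AE tables are crude too, and length of observation is not reported by period.

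Several stronger readings are tempting and are not supported:

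- *That the arms are not comparable.* With similar stopping and withdrawal the ratio is unaffected, and the documents give no rates by arm.
- *That the SAP breaks its own convention.* SAP 5.3 says "All Post-treatment medications taken during the Post-Treatment period will be summarized by treatment group based on the subset of patients in the SAF", but that subset is not defined. It need not mean patients who entered the period.
- *That a period-specific SAF was clearly intended, or clearly ruled out.* The word respective in 5.8.1 and the plural SAFs in 5.8.7 could hint at one, but none is defined.
- *That patients not reached by phone are counted as having no JR.* The denominator for that summary is simply unstated.
- *That an entrants-only denominator is the cure.* It leaves time unequal (Step 5) and selects patients after randomization.

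**Conclusion.** The point holds in a limited form. On the only SAF defined, post-treatment AE and JR percentages count patients with no time at risk and mix follow-up from 0 to about 280 days. They understate risk among entrants by the share who never enter. The 20% figure is an upper case: it takes the planning dropout rate and assumes that every dropout leaves the study before the period begins.

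Distortion between arms is conditional. Its direction depends on whether early stoppers leave or stay, and the ratios of 1.13 to 1.29 and 0.92 to 0.85 rest on assumed shares and a constant hazard. Its actual size cannot be known from the documents.

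For JR only the period-split percentage is affected. The main gap is AEs, including the sympathetic and peripheral sensory AESIs, which have no time-adjusted summary. No efficacy conclusion changes, but the SAP should be amended so that these safety tables can be read correctly.

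**What to change.** Keep the SAF percentages and change the SAP as follows.

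1. In 5.8.1 and 5.8.2 add, by period and arm: the number of patients entering the period, person-time, and patients with event per 100 patient-years, with time counted from the start of the period to the first event or the end of the period.
2. In section 5 (Period of Observation), state whether the last dose of study drug means the SC or the oral dose.
3. In 5.8.7, for JR reported at the end-of-study phone call, show the number contacted and the number not reached.

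The cost is SAP wording, one derived variable (days observed per period) and a few extra table columns. No new data are needed. One limit remains: if risk changes with time since the last dose, a single rate averages over windows of different length, so the person-time columns should be read with the numbers entering.
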